Initial Graft Tension and ACL Surgery

PI: [name]

**Rhode Island Hospital
Providence RI 02903**

ClinicalTrials.gov identifier: NCT00434837

Updated: 09/10/2019 (after NIH funding received for 15-year follow-up; R01-AR074973)

SPECIFIC AIMS

The primary objective of this prospective, randomized, double-blinded, controlled study is to assess OA progression following ACL reconstruction (ACLR), and to determine how the initial tension applied to the graft at the time of surgery may influence disease progression. ACLR is commonly performed to restore joint function and to decrease the risk of post-traumatic osteoarthritis (OA) in the ACL-deficient knee. However, clinical studies suggest that the outcome is highly variable, and that OA often progresses despite ACLR. The tension applied to the graft at the time of ACLR fixation (“initial graft tension”) affects knee kinematics and the distribution and magnitude of contact stress, which in turn, is thought to influence articular cartilage damage. The effects of low- and high-initial graft tensions on graft healing and articular cartilage degeneration following ACLR are unknown and are currently under investigation in this study. Over the past funding cycle, ACL-injured subjects (108 patients) and matched controls (60 subjects) were recruited and enrolled. Short-term (≤ 84 months) post-surgical evaluations have been performed. The objective of this update is to prospectively obtain valuable long-term (15 year) follow-ups on this captured patient/control population. We intend to follow these patients a minimum of 15 years. These long-term data will allow us to establish not only the incidence of OA after ACLR following an isolated ACL tear, but whether changing the initial graft tension can decrease this risk.

This study is designed to compare two common initial graft tension protocols for ACLR that influence joint contact mechanics. The first treatment group consists of patients whose grafts were tensioned to restore the normal anterior-posterior displacement of the tibia relative to the femur (“AP laxity”) at the time of surgery (i.e. AP laxity equal to that of the contralateral normal knee; the “low-tension” treatment). The second treatment group consists of patients whose grafts were tensioned to over-constrain the joint (i.e. AP laxity 2mm less than that of the contralateral knee; the “high-tension” treatment). In the last funding cycle, we have shown that the initial joint contact conditions between these two groups are significantly different in cadavers³⁹, and that the associated laxity differences in patients are different *in vivo*. The two treatment groups are being compared to a third matched control group. Fifty-four subjects were enrolled into each group. With this update, they will be followed 180 months after surgery. We are planning to follow these patients for a minimum of 15 years. Significant changes in cartilage integrity are expected within this long-term time frame in this patient population^{26,35,50}.

Radiographic assessment of joint space narrowing is the only validated indicator of structural change used to evaluate OA progression in clinical studies, and it will continue to be the primary outcome measure of cartilage damage⁶⁷. MR images of the articular cartilage and associated knee joint structures will provide secondary structural biomarkers for the early detection of OA³¹. MRI is being used to directly measure changes in cartilage thickness in the load bearing regions^{11,12}, while joint integrity will be assessed using the Whole Organ Magnetic Imaging Score (WORM score)⁵⁶. Using these imaging-based outcome measures, we will test the primary hypothesis:

- *Tibiofemoral joint space width (via radiography) and cartilage thickness (via MRI) in the reconstructed knees of the “high-tension” treatment group will be equal to that of the control group, while the joint space width and cartilage thickness in the “low-tension” treatment group will be significantly less than that of the control group 15 years after surgical reconstruction of the anterior cruciate ligament.*

Surgical outcome will also be assessed via: 1) patient-oriented outcome scores^{59,76}, 2) AP laxity (an indicator of graft integrity^{6,44} and knee kinematics²³), 3) isokinetic strength (an indicator of dynamic knee function¹⁶), and 4) clinical outcome scores^{48,78}. Analysis of primary and secondary outcomes will enable us to determine the long-term effects of initial graft tension on cartilage status and knee joint function, and to evaluate the relationships between longitudinal changes that occur in tibiofemoral (TF) joint space (x-ray), cartilage thickness (MRI), general MRI scores (WORM score), knee laxity (KT-1000), strength (Biodex strength test, 1 legged hop test) and patient-oriented outcome scores (SF-36, Knee Osteoarthritis Outcome Score). In the past funding cycle, data were obtained from ACL-reconstructed patients pre-operatively, immediately post-operatively, and after 6, 12, 36, and 84 months of healing. From the control group data were obtained at the time of recruitment and at 12, 36, and 84 months. In this update, additional evaluations will be performed 144 and 180 months in the ACLR and control subjects, a time frame in which cartilage damage should become prevalent in the ACLR patient population. We intend to follow these patients for a minimum of 15 years.

RESEARCH DESIGN AND METHODS

1. Overview of Research Design

This investigation is designed as a prospective, randomized, double-blinded clinical study evaluating the effects of two different initial tension conditions applied to an ACL graft at the time of fixation on healing using biomechanical, clinical, and patient-oriented outcome measures. The primary outcome is evaluating the progression of OA via objective radiographic measurements of joint space narrowing. We are also assessing temporal changes in cartilage thickness, and the integrity of various knee joint structures using MRI. We will test the hypothesis that tibiofemoral (TF) joint space width (via radiography) and cartilage thickness (via MRI) in the reconstructed knees of the “high-tension” treatment group will be equal to that of the control group, while the joint space width and cartilage thickness in the “low-tension” treatment group will be significantly less than that of the control group 15 years after surgical reconstruction of the ACL. We intend to follow these patients for a minimum of 15 years.

Surgical outcome will also be assessed via: 1) patient-oriented outcome scores^{59,76}, 2) AP laxity (an indicator of graft integrity^{6,44} and knee kinematics²³), 3) isokinetic strength (an indicator of dynamic knee function¹⁶), and 4) clinical outcome scores^{48,78}. Analysis of primary and secondary outcomes will enable us to determine the long-term effects of initial graft tension on cartilage status and knee joint function, and to evaluate the relationships between the longitudinal changes that occur in TF joint space narrowing (x-ray), cartilage thickness (MRI), general MRI scores (WORM score), knee laxity (KT-1000), thigh strength (Biodex strength test, 1 legged hop test) and patient-oriented outcome scores (SF-36, Knee Osteoarthritis Outcome Score). In the past funding cycle, data were obtained prospectively from ACLR patients and matched control subjects from the time of recruitment (pre-operative) through 84 months of healing. In this update, additional evaluations will be performed 144 and 180 months, a time frame in which cartilage damage should become more pronounced in this patient population. These analyses will shed light on potential factors that may play a role in the degenerative process and long-term outcome.

2. Subjects

108 ACL-injured patients, who required ACLR, were recruited during the first three years of the initial funding cycle. It was our intent to identify patients with isolated ACL injuries while minimizing confounding variables. To do this, all patients who came through the sports medicine clinics of University Orthopaedics Inc between 02/09/2004 and 02/08/2007 were considered for the study. All who met the pre-operative inclusion criteria and did not meet the exclusion criteria (Table 1) were asked to participate and provide their informed consent. Additional “intra-operative” inclusion/exclusion criteria were then evaluated at the time of surgery (Table 1). If the patient remained eligible, minimum likelihood allocation was used to randomly assign each subject to one of the two initial graft tension groups¹. Randomization was performed to achieve balance between the treatment groups for characteristics that would influence long-term outcome and cartilage health; age, gender, race, and activity level (Tegner score). The number of patients who injured their ACL and choose ACLR within the clinical practice was documented, and the reasons for excluding subjects were recorded.

60 “matched” control subjects, who had no known history of knee injury or symptoms of arthritis, were recruited from the hospital campus, local colleges, and Providence community. They were selected to match the frequency of individuals by age (± 5 years), gender, race, and activity level (Tegner score ± 1 point). The subjects’ knees were evaluated by clinical exam at a screening visit. Subjects were not included in the control group if they have a side-to-side difference in AP laxity greater than or equal to 2-mm (KT-1000), a Tegner activity score less than 5⁶⁹, or if they meet any of the other exclusion criteria (Table 1). It was our intent to establish a control group that matched the characteristics of the population at risk to ACL injury.

3. Research Design

This study is designed as a prospective, randomized, double-blinded controlled trial comparing the outcome of two different initial tension conditions applied to the ACL graft at the time of surgery, and to determine the relationship between factors that may predict who will be risk for OA. The project statistician and the operating surgeon initially knew a patient’s assignment at the time of surgery, however, the

surgeon was not allowed to review the assignment once the surgery was completed, and the statistician was not allowed to review the assignments until after all the subjects were enrolled. The patient, the therapist performing the follow-up assessments, the AP laxity and isokinetic strength testing, the engineer performing the radiographic joint space width and cartilage thickness measurements, and the radiologist performing the WORM scoring will continue to be blinded from the subject's group assignment throughout the study. An intent-to-treat protocol is being utilized. All subjects randomized to each group are being followed, and all available data will be analyzed even if the graft fails, if the subject is unwilling to perform a particular follow-up test (missing data), or if a subject completely drops out of the study.

Table 1. Inclusion/exclusion criteria for patient enrollment.

Treatment Groups (Hi- and Lo-tension)	
Inclusion Criteria	Male or female subjects between the ages of 15 and 50 years with unilateral ACL injury.
	Candidates for ACLR using bone-PT-bone or four-stranded hamstring tendon autograft.
	A Tegner activity score ⁶⁹ ≥ 2 .
	Minor tears of the menisci that require minimal treatment (<1/3).
Exclusion Criteria	An ACL tear occurring more than 12-months prior to the 1st office visit.
	Previous injury to either knee.
	Increased clinical laxity of the MCL, LCL, or PCL as compared to the control knee.
	Evidence of degenerative arthritis on radiographs.
	Women who are pregnant.
	Diseases that predispose a patient to articular cartilage damage.
	Moderate sized fissures or lesions in articular cartilage.
	Meniscal tears requiring partial meniscectomy involving more than 1/3 of meniscus.
Control Group	
Inclusion Criteria	Male or female subjects between the ages of 18 and 50 years.
	A Tegner activity score ⁶⁹ ≥ 2 .
Exclusion Criteria	Previous injury to either knee.
	Increased laxity of the MCL, LCL, or PCL compared to the control knee.
	Evidence of degenerative arthritis on radiographs
	Women who are pregnant.
	Diseases that predispose a patient to articular cartilage damage (e.g. rheumatoid arthritis, osteoporosis, metabolic diseases).

Patients were included in the study if they were candidates for autogenous ACLR with either a bone-patellar tendon-bone or a 4-stranded hamstring tendon graft. Due to the popularity of these graft types, both were included to extend the recruitment base. It should be noted that we initially proposed to include only bone-patellar tendon-bone grafts in the study. However, the recent surge in popularity of the hamstring tendon graft and the need to extend our recruitment based convinced us to include this procedure after eight months of recruiting candidates for patellar tendon autograft only. This was justified since recent biomechanical studies have shown that the structural properties of the patellar tendon autograft are equal to that of the 4-stranded hamstring tendon autograft ⁷⁹. Likewise, the in-situ forces, the passive load-displacement response, and dynamic kinematics of reconstructed knees with patellar tendon and 4-stranded hamstring tendon grafts are equivalent ^{68,82}. Recent prospective randomized clinical trials comparing these two graft types have shown that functional and patient-oriented outcomes are equivalent ^{2,3,19,33,34,41,42,49,62,64}. Finally, the two graft tension procedures in this study produced the same AP laxity values between graft types. Other than graft type, all surgically related parameters were standardized across surgeons. The same surgical instrumentation within each graft type was used to ensure that intra-articular graft placement was similar between patients. "Aperture" fixation interference screws were used to standardize graft fixation. Another variable, which could possibly affect outcome, is the rehabilitation program prescribed following surgery ⁸. Recent data comparing commonly used rehabilitation protocols has shown that rehabilitation with either an "accelerated" or "non-accelerated" program would produce the same clinical, functional and patient oriented outcomes ^{5,8}. Nonetheless, all

subjects were required to follow the same “accelerated” rehabilitation program, which was geared to get patients back to sport within 6-months.

4. Independent variable (Initial graft tension condition based on AP laxity)

Two initial graft tension conditions are being compared; 1) a graft tension that restored the AP laxity of the ACLR knee to that of the contralateral ACL intact knee (the “low-tension” treatment), and 2) a graft tension that reduced the AP laxity by 2mm in comparison to the contralateral ACL-intact knee (the “high-tension” treatment) at the time of surgery. Thus, a graft tensioning protocol that is based on the AP laxity at the time of graft fixation (“laxity-based” approach) was selected for this study instead of a “tension-based” approach³⁹. It has been shown that the graft tension immediately after fixation is dependent on the knee angle and magnitude of tension applied immediately prior to fixation and that an increase in graft tension reduces knee laxity^{17,38,39,81}. The laxity-based approach implies that the tension in the graft is adjusted to produce an AP laxity value that is equal to or less than that of the contralateral normal knee, depending on a subject’s group assignment. A tension-based approach (e.g. 20 N, 40 N, etc) was not used for this study because the amount of force required to restore AP laxity would be subject specific¹⁵, and prone to other sources of error^{40,75}. Although a laxity-based tensioning approach may require a variety of tension levels to be applied across patients within a treatment group, the tension applied to the graft in an effort to recreate normal AP laxity would be less than that required to over-constrain the joint, hence the terminology of “low-tension” versus “high-tension”. It is known that AP laxity values are significantly less when the graft is tensioned at 30° in comparison to full extension (0°), thus it is easy to control AP laxity by tensioning the graft at different knee flexion angles. The two initial tension treatments were controlled as follows. For the “low-tension” treatment, the tension was applied to the graft with the knee at 0° flexion (full extension). After an initial tension level was selected, the knee was flexed to 20° and an AP laxity test was performed (using the KT-1000S). The tension was adjusted iteratively until the AP laxity of the ACLR knee matched that of the contralateral limb (± 1.0 mm). For the “high-tension” treatment, the tension was applied with the knee at 30° of flexion. The tension was adjusted until the AP laxity value at 20° of flexion is 2mm (± 1.0 mm) less than the contralateral limb. The graft was then fixed with an interference screw, and the laxity value rechecked to ensure that the initial tension condition was maintained during fixation. The difference in knee flexion angle at which the tension was applied between the high-tension treatment as compared to the low-tension treatment assists in producing a lower AP laxity value at 20°. Thus, higher forces are produced in the graft across the full range of knee flexion angles^{17,38,81}. Another advantage of using AP laxity at the time of graft fixation to control graft tension was that changes in AP laxity can be measured at the post-operative follow-up visits as well. It would not be possible to directly measure graft forces immediately after graft fixation and at the follow-up visits if a tension-based approach was utilized. In our pilot analysis we demonstrated that it is possible to restore normal laxity (at ± 90 N shear force) and to reduce AP laxity by at least 1.5mm (at ± 90 N shear force) compared to the normal side using these initial graft-tensioning protocols. For the patients enrolled in the current study, the mean (\pm standard deviation) laxity difference at 133 N (reconstructed knee – control knee) for the high-tension group was -2.1 (± 0.69) and -0.3 (± 1.29) mm for the high- and low-tension groups, respectively, with the “manual maximum” test²³. The required difference in AP laxity at the time of graft fixation between tensioning techniques (the independent variable) was achieved.

5. Outcome Measures (dependent variables)

In this comprehensive evaluation of the effects of initial graft tension on ACLR, five sets of outcomes are under examination: 1) Imaging assessment of OA progression; 2) Patient-oriented outcomes; 3) Knee kinematics; 4) Dynamic joint function; and 5) Clinical outcome. Within each category (Tables 2&3), at least one test will be performed. In those categories featuring two or more tests, the first will be considered the primary test of that category.

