Treatment Comparisons - Primary Outcome Measure: Repeated measures analysis of variance will be used to evaluate differences among treatment groups with respect to temporal changes in joint space width (i.e. joint space narrowing). The statistical model will include fixed factors representing treatment group (“low-tension”, “high-tension” and “control”), limb (operative vs. contra-lateral or two controls), location (medial vs. lateral), time (baseline, 12-, 36-, 60-, and 84-month), and their interactions. If significant interactions are detected, simple effects will be compared using the Student-Newman-Keuls procedure based on the appropriate error terms⁸⁰. Because one of the repeated factors (i.e. time) is quantitative, orthogonal polynomial will be used to partition the time effect into its individual quantitative components (i.e. linear and quadratic). The significance of these orthogonal contrasts will be used to evaluate the linearity (or non-linearity) of the temporal trend associated with degeneration. Analyses will be performed using SAS, PROC MIXED⁵² that allows for covariance structures other than compound symmetry (e.g. unstructured, autoregressive, spatial power law). It is expected that the variability across subjects may increase across time due to only a subset of individuals exhibiting degeneration, which would violate the standard homogeneity of variance assumptions. The normality assumption will be examined based on residuals using normal probability plots and the Wilk-Shapiro test. If necessary, data will be transformed prior to analysis in order to satisfy the distributional assumptions.

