Justification of Sample Size based on Primary Outcome Measure: The estimated sample size of 35 assessable subjects per group through the 84-month study period will result in having sufficient power ($1-\beta=0.80$ using $\alpha=.05$) to detect a mean difference between groups of 0.25 mm in joint space narrowing over the 84-month study period. This estimated difference is based on the following rationale. Previous studies have shown that patients with primary OA exhibit an estimated 0.3-mm change in joint space width per year^{51,63}. Since we will be studying patients at the time of OA onset, we will assume that patients who undergo initial changes will exhibit an average joint space narrowing of 0.1 mm per year, or a total of approximately 0.6 mm over the 84 months. This estimate was conservatively adjusted based on the study by Johma et al, who found that only 50% of the subjects that undergo ACL reconstruction after injury exhibit early degenerative changes following surgery⁵⁰. After taking into account that only a subset of subjects randomized may exhibit OA, the resulting mean difference is decreased to be 0.25-0.30 mm over the 84-month study period. An additional consequence of only a subset of the patients that are randomized exhibiting degeneration is an increase in the variability encountered across subjects with respect to joint space narrowing. The variability estimate used in our computations ($\sigma_{\Delta}=0.35$ mm) resulted from increasing the estimate derived from the literature for a group of subjects with OA in order to reflect our expected mixture of two subsets of subjects. Based on each subset having $\sigma_{\Delta}=0.20$, with 50% of the patients exhibiting narrowing a total of 0.6 mm and 50% showing no degeneration, the resulting overall estimated $\sigma_{\Delta}=0.35$. Assuming joint space width at baseline is approximately 4.5 mm³⁰, this detectable mean difference (0.25 mm) represents an approximate 5% change between the treatment groups in the mean rate of degeneration. We recruited 54 subjects per group in an effort to have 46 assessable subjects per group at the three-year follow-up visit based on the estimated 15% dropout rate^{4,7}. We have more than met this goal (3% drop out in our treatment groups and 15% drop out in our control group at 3 years). For the proposed 180-month follow-up we expect that we will have at least 35 patients/subjects in each group (20% drop out rate of subjects currently enrolled).

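### The primary hypothesis predicts that high tension equals a non-randomised control, but equality has no criterion, only difference tests are planned, and the randomised high-versus-low contrast is not named as deciding

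*Combined protocol and SAP*

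**What the plan says.** **Hypothesis.** Specific Aims labels as primary the prediction that, 15 years after surgery, joint space width and cartilage thickness in the high-tension "treatment group will be equal to that of the control group, while the joint space width and cartilage thickness in the" low-tension group will be significantly below control. Section 1 (Overview of Research Design) presents it as something to be tested: "We will test the hypothesis that tibiofemoral (TF) joint space width (via radiography) and cartilage thickness (via MRI", followed by the same two predictions.

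**Groups.** Under section 2 (Subjects), only the allocation between the two tension groups was random. The controls "were recruited from the hospital campus, local colleges, and Providence community" and were frequency-matched on age, gender, race and activity level.

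**Design comparison.** Specific Aims also says: "This study is designed to compare two common initial graft tension protocols for ACLR". Section 3 describes a trial "comparing the outcome of two different initial tension conditions applied to the ACL graft at the time of surgery". The long-term aim is to learn whether a change of initial tension lowers the risk of OA.

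**Analysis.** Section 8 fits a repeated-measures model to joint space width with group, limb, location and time. Control is listed as one of three treatment groups, and the listed times end at 84 months. Then: "If significant interactions are detected, simple effects will be compared using the Student-Newman-Keuls procedure".

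**Sample size.** The justification takes 35 assessable subjects per group, power 0.80 and alpha 0.05 for a 0.25 mm difference in narrowing over 84 months. The SD of change is 0.35 mm, built from two subsets, each with SD 0.20, "with 50% of the patients exhibiting narrowing a total of 0.6 mm and 50% showing no degeneration". The 0.25 mm "represents an approximate 5% change between the treatment groups in the mean rate of degeneration".

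No section gives a margin, a confidence-interval rule or any other criterion for equality.

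**The concern.** There are two gaps.

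1. A test of difference cannot establish equality. Without a criterion, the high-tension half of the hypothesis can be supported only by failing to find a difference, and that becomes easier as numbers fall or variability rises.

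2. The hypothesis is made of two comparisons with a non-randomised group. That low differs from control while high does not is not evidence that high differs from low. The aim, whether tension alters OA risk, needs the high-low contrast. That contrast is the one protected by randomisation, yet it is absent from the primary hypothesis and is not named as the comparison that decides the conclusion.

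If the conclusion followed the hypothesis as worded, a moderate deficit in the high-tension arm could be reported as equality with uninjured knees. A benefit of high tension could also be read from a pattern that arises when tension has no effect.

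**Working it through.** **Inputs.** From the sample-size justification: n = 35 per group, difference 0.25 mm, SD of change 0.35 mm, within-subset SD 0.20 mm, half of patients narrowing 0.6 mm, all at 84 months. Two-sided 0.05 is assumed because sidedness is not stated. Each subject is reduced to one change score; limb, location, time and the actual interaction gate are not modelled.

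**1. The plan's own figure.** The mixture SD is √(0.20² + 0.5 × 0.5 × 0.6²) = √0.13 = 0.3606, rounded in the plan to 0.35. A two-sample t test with 68 df has noncentrality d / (SD × √(2/n)). At SD 0.35 this is 0.25 / 0.0837 = 2.99, power 84%. At SD 0.3606 the power is 82%. The stated 0.80 is reproduced as one unadjusted test of difference. It says nothing about showing equality.

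**2. Non-significance read as equality.** Probability that high versus control is non-significant:

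| True high-tension deficit | SD 0.35 in both groups | Mixture arm, control SD 0.20 |
|---|---|---|
| 0.125 mm | 69% | 51% |
| 0.15 mm | 58% | 37% |

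The mixture arm lets a share deficit/0.6 of patients narrow by 0.6 mm. The control SD of 0.20 assumes that no control narrows. At SD 0.35 the 95% CI half-width is 1.9955 × 0.0837 = 0.17 mm, so even an observed difference of zero leaves deficits up to 0.17 mm unexcluded.

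**3. The hypothesised pattern with no tension effect.** In Student-Newman-Keuls with three groups and 102 df, q₃ = 3.364 and q₂ = 2.805. At a pooled SD of 0.35 the standard error of a mean is 0.35/√35 = 0.0592. The widest gap must therefore exceed 3.364 × 0.0592 = 0.199 mm, and an adjacent gap 2.805 × 0.0592 = 0.166 mm. Low and high can fall on opposite sides of significance against control while only slightly more than 0.199 − 0.166 = 0.033 mm apart.

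Giving both arms the same true deficit, the simulated probability that low is significantly below control and high is not different is:

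| Shared deficit (mm) | SD 0.35 in all groups | Mixture, control SD 0.20 |
|---|---|---|
| 0.10 | 6.0% | 10.2% |
| 0.15 | 9.1% | 13.7% |
| 0.20 | 9.6% | 10.8% |
| 0.25 | 6.7% | 5.0% |
| 0.30 | 3.2% | 1.3% |

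A direct high-low t test errs in that direction in 2.5%. The 0.30 mm row is the plan's own 50% × 0.6 mm; there the excess has largely or wholly gone. At 0.15 to 0.25 mm, the Student-Newman-Keuls high-low comparison is itself non-significant in 80-81% of these patterns (SD 0.35) or 67-75% (mixture).

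**4. What changes at 180 months.** The documents give no 180-month SD and no narrowing rate for controls. As an assumption, let the plan's narrowing continue in affected patients: 0.6 × 180/84 = 1.29 mm, or 0.1 mm × 15 years = 1.5 mm, with no control narrowing. With 50% affected, the SD is √(0.04 + 0.25 × 1.29²) = 0.67 to √(0.04 + 0.25 × 1.5²) = 0.78. The false pattern then appears in fewer than 0.1% of trials. If 10-30% are affected it appears in roughly 6-18%.

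High-low power for 0.25 mm is about 63% at an assumed SD of 0.45 and about 26% at 0.78. For a proportionally scaled difference, 0.25 × 180/84 = 0.54 mm, it is about 91% at SD 0.67 and 81% at 0.78.

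**The case against.** The strongest reply is that the hypothesis is a scientific prediction, not a decision rule. Section 8 sets out to evaluate differences among groups and nowhere says that non-significance will be reported as equality. A reader might infer that the plan commits itself to that error. The documents do not support this; the harm arises only if the conclusion follows the hypothesis as worded. But both Specific Aims and section 1 say that this hypothesis will be tested, and no other route to a conclusion about equality is given.

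A reader might also infer that the randomised comparison has been overlooked. It has not. High versus low is the stated design comparison and a Student-Newman-Keuls pair, and it may be what the powered 0.25 mm refers to, although that wording is ambiguous because control is listed among the treatment groups. The interaction gate applies to the control comparisons too, so it does not single out high-low. The planned high-low test would also usually be non-significant when the misleading pattern occurs. What remains is that the two could disagree and nothing says that high-low decides.

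Finally, the rates in steps 2 and 3 use 84-month inputs while the hypothesis is at 15 years. That limit stands. So does the point that a single 180-month contrast is one defensible choice of primary; the documents do not compel it.

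**Conclusion.** The concern holds in limited form. Equality has no criterion, the plan tests and powers only differences, and the contrast that answers the aim is not named as deciding. This follows from the text and needs no simulation.

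The size is illustrative. It rests on 84-month inputs, 35 per group and a single change score: 69% or 58% non-significance at a true deficit of 0.125 or 0.15 mm (SD 0.35), and a false pattern in about 6-10% (SD 0.35) or 5-14% (mixture) at shared deficits of 0.10 to 0.25 mm, against 2.5%. It would be tempting to quote these as the error risk of the 15-year analysis, but step 4 shows that the risk could be negligible or somewhat higher, depending on how many patients narrow. Nor is the sample size shown to be wrong as a test of difference.

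The gap should be closed before the 180-month analysis. It affects what may be concluded, not the data.

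**What to change.** - Name high minus low in reconstructed-knee joint space width change at 180 months as the primary contrast. Estimate it with a 95% CI in the section 8 mixed model, not conditional on an interaction test.
- Extend the model's time factor to include 144 and 180 months.
- Report high minus control and low minus control as estimates with CIs, and state that equality will not be concluded from non-significance.
- Claim equivalence only against a margin justified in advance. The documents contain none; 0.25 mm is the difference the plan aims to detect, not one it calls negligible.
- Do not cite the 84-month power (84% or 82% for 0.25 mm) for the 180-month contrast. State the assumed 180-month SD and show power over a range, as in step 4.
- Date the change and disclose that it follows publication of the 7-year results (note of 9/29/2017), and that section 3 allowed the statistician to see assignments once enrolment was complete.

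The cost is analysis-plan wording, the extended time factor and a few ESTIMATE statements. No data collection changes. The main price is lateness, which disclosure makes visible but does not remove.
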